10.4. Efficacy Analysis Methods for Primary and Secondary Endpoints

10.4.1. Analysis Study

10.4.1.1. Primary Endpoint PFS

Progression Free Survival, as assessed by the investigator, will be analyzed in the ITT population, comparing the 2 treatment arms (Arm A and Arm B) at an overall 1-sided 0.025 significance level using the log-rank test stratified by the randomization stratification factors: age group, FLIPI-1 score and ECOG performance status score. Distribution of PFS will be summarized for each treatment arm using the Kaplan-Meier (KM) method. The estimate of the hazard ratio between the two arms and its corresponding 95% CI will be computed using a Cox proportional hazards model stratified by the randomization stratification factors. In stratified efficacy analysis, small strata are combined to form bigger strata with ≥ 10 events and ≥ 40 patients in each stratum.

PFS is defined as duration from the date of randomization to the date of first documentation of disease progression or date of death due to any cause, whichever is first reported, prior to the use of subsequent anti-cancer therapy. Subjects who initiated subsequent anti-cancer therapy before disease progression or death will be censored at the last adequate disease assessment before the use of subsequent anti-cancer therapy. Subjects who are progression-free and alive, or have unknown status will be censored at the last adequate disease assessment. Subjects with no postbaseline disease assessment will be censored at randomization date. Adequate disease assessment is defined as having sufficient evidence to correctly indicate that progression has or has not occurred.

Supplementary/sensitivity analyses may be conducted using different censoring rules and will be described in the SAP.

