## 1.2 Endpoints

### 1.2.1 Primary Endpoint

The primary efficacy endpoint is progression-free survival (PFS) as assessed by the investigator. PFS is defined as the time from date of randomization to the date of the first documented progressive disease (PD), as defined on the Revised Response Criteria for Malignant Lymphoma (Cheson 2014, Lugano Classification), or death due to any cause, whichever occurs first.

The estimand corresponding to the primary efficacy endpoint (PFS per investigator assessment) is the treatment effect (hazard ratio: ibrutinib + rituximab versus placebo + rituximab) in all randomized subjects with treatment naïve FL regardless of premature discontinuation of study treatment, as measured by the earlier occurrence of progressive disease per the investigator assessment or death, whichever occurs first (Table 1). The details of handling strategies of the intercurrent events in the PFS primary and supplementary analyses for US and for Other Regions are in Table 2.1 and Table 2.2.

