**Table 6. Definitions and Analyses for Endpoints**

Endpoint	Definition	Analysis Method
Primary Endpoint		
PFS assessed by investigator	
Time from the date of randomization to the date of the first documented disease progression (PD) or death due to any cause, whichever occurred first, prior to the initiation of subsequent anti-cancer therapy, regardless of premature discontinuation of study treatment. Stem cell transplant is not considered a subsequent anti-cancer therapy for PFS.
 
For the evaluation of disease progression, an adequate post-baseline assessment is defined as an assessment where there is enough evidence to indicate the subject had or had not progressed based on Cheson 2014 (Lugano Classification Criteria).
 
Subjects without baseline or post-baseline disease assessment will be censored at the date of randomization.
	
Primary Analysis:
 
Subjects without a PFS event will be censored at the date of the last adequate post-baseline assessment showing no evidence of PD.
 
Stratified log-rank test is the primary analysis comparing treatment effects. Cox proportional hazards model stratified by the pre-specified stratification factors will be used to estimate hazard ratio (HR) and its associated confidence interval (CI). In addition, Kaplan-Meier estimates and median PFS with its associated CI will be displayed. Brookmeyer-Crowley confidence interval based on the log-log-transformed Greenwood variance estimate will be calculated for median PFS (mPFS); KM estimates at selected landmark points will also be provided.
 
Handling strategies to address intercurrent events in Section 1.2.1 will be implemented.
 
Primary Analysis Censoring Rules
 
 
A. Treatment policy strategy will be used to handle the intercurrent events of discontinuation of study treatment; i.e ignore the intercurrent events and use time to PD or death, whichever occurs first regardless of discontinuation of study treatment.
 
B. Hypothetical strategy will be used to handle the intercurrent events of subjects who received anti-cancer treatment; i.e. subjects who initiated subsequent anti-cancer treatment will be censored at the last adequate post-baseline disease assessment showing no evidence of PD before the use of subsequent anti-cancer therapy.
 

 An AbbVie Company	PCYC-1141-CA Analysis Study Statistical Analysis Plan	Page 20 of 33

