		
C. Composite variable strategy will be used to handle the intercurrent events of death due to COVID-19 without PD; i.e. consider COVID-19 deaths without PD a PFS event.
 
D. Subjects who missed two or more consecutive overall disease assessments will be censored at the last adequate post-baseline disease assessment prior to the first missed disease assessment, regardless of whether or not a PFS event subsequently occurs. The algorithm to define missing 2 or more consecutive assessments is described in Appendix 6.1. This particular censoring rule will be applied to the primary analysis for US regulatory purposes only.
 
The Sponsor will extend follow-up time to accrue additional PFS events to make up for the potential impact of COVID in accordance with FDA’s COVID-19 guidance (FDA guidance, June 2020).
 
Sensitivity/Supplementary Analyses:
 
 
1. Non-stratified log-rank test and non-stratified Cox regression model. Same censoring convention as the primary analysis.
 
2. Change on the estimand’s strategy for handling death due to COVID-19 without PD from composite variable strategy to hypothetical strategy; i.e. subjects who died due to COVID-19 without PD will be censored at the last adequate post-baseline disease assessment.
 
3. Use time to PD or death regardless of whether subjects missed any overall disease assessments. This will be applied to the primary analysis for Other Regions and is included as a sensitivity analysis for the US.
 
4. PFS analysis based on the ITT principle. Ignore the intercurrent events (including the use of subsequent anti-cancer therapy) and use time to PD or death regardless of whether subjects missed
 

Endpoint	Definition	Analysis Method
		
any overall disease assessments.
 
5. PFS assessed by Independent Review Committee (IRC); conduct same analyses as specified for the primary and sensitivity/supplementary analyses for PFS assessed by investigator.
 
Subgroup analysis:
 
Hazard ratio and its 95% CI based on unstratified Cox regression model for each subgroup. A forest plot will be provided. Same censoring convention as the primary analysis.

Secondary Endpoints		

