## 6 APPENDICES

### 6.1 Algorithm for Defining $\geq 2$ Consecutive Missing Assessments

This algorithm is used for the PFS primary analysis for US regulatory submission and for the PFS sensitivity analyses for Other Regions.

This study has 2 planned imaging schedules: every 4 cycles (1 cycle = 28 days) from Cycle 5 through Cycle 37, and every 6 cycles afterwards (see [Table 8](#) below). Based on the change between the schedules, one transition of the imaging schedule (time period 2 in [Table 8](#) below) is described as follows:

- When the adequate non-PD assessment occurs at Cycle 33, the next two subsequent assessments are planned at Cycle 37 (+4 cycles) and Cycle 43 (+6 cycles), respectively.

This algorithm will follow two steps in sequence:

1. Step 1 (Columns 2-4 in [Table 8](#)): Calculate the study day of the adequate non-PD assessment. Map the adequate non-PD assessment to a closest scheduled visit based on the study day using the midpoint time period window (see footnote of [Table 8](#) for details). Once the assessment is mapped to a scheduled visit, the imaging interval for the next two subsequent consecutive visits can be decided based on the planned imaging schedule.
2. Step 2 (column 5 in [Table 8](#)): Calculate the maximum gap in days allowed for the next two subsequent visits based on the planned imaging interval plus the specified window (+/- 28 days) for each visit.

If the gap between the adequate non-PD assessment and the next adequate assessment or death exceeds the maximum gap, the subject has a  $\geq 2$  consecutive missing assessments and its PFS will be censored at the last adequate non-PD assessment before the missing interval. If there are 2 more missing intervals, the PFS will be censored at the last adequate assessment before the first missing interval. If the first missing interval occurs right after the randomization date, then PFS will be censored at the randomization date.

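### Read literally, the no-assessment rule for PFS censors at randomization a subject who dies before any post-baseline scan; this conflicts with the PFS definition, and the plan does not say which rule prevails

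*SAP*

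**What the plan says.** SAP 1.2.1 defines PFS as time to progression "or death due to any cause, whichever occurs first". Table 6 repeats this as "the first documented disease progression (PD) or death due to any cause, whichever occurred first", before any subsequent anticancer therapy. The same table cell then states: "Subjects without baseline or post-baseline disease assessment will be censored at the date of randomization". Protocol 10.4.1.1 has the counterpart: "Subjects with no postbaseline disease assessment will be censored at randomization date". The protocol sentence just before that one does carry a survival condition: "Subjects who are progression-free and alive, or have unknown status will be censored at the last adequate disease assessment".

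Other parts of the SAP bear on the same subjects:

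- The Primary Analysis entry in Table 6: "Subjects without a PFS event will be censored at the date of the last adequate post-baseline assessment showing no evidence of PD".
- Rule C of the primary censoring rules: "consider COVID-19 deaths without PD a PFS event", with no scan required.
- Item 3 of the sensitivity/supplementary list, which is the primary rule for Other Regions: missed assessments do not stop a progression or death from counting.
- Rule D with Appendix 6.1, for the US analysis: the gap runs from the last adequate non-progression assessment to the next adequate assessment or to death, and too long a gap leads to censoring. Table 8 allows 280 days in its first time period. For gaps at the start of the study: "If the first missing interval occurs right after the randomization date, then PFS will be censored at the randomization date".

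**The concern.** A subject who dies with no post-baseline assessment meets both the event definition and the censoring sentence in the same table cell. A programmer who follows the censoring sentence gives that subject zero follow-up and no event. One who derives events first records a death. The two choices give different primary-endpoint data, and a different date on which 200 events is reached.

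If such deaths are dropped and are more frequent in one arm, the comparison is biased in favour of that arm. No listed analysis is certain to show the difference. Sensitivity items 3 and 4 set aside missed assessments but do not explicitly switch off the no-assessment sentence, and item 5 repeats the same rules on IRC data.

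**Working it through.** **1. The rules side by side.** Take a subject with no post-baseline assessment and no new anticancer therapy. Assume that Appendix 6.1 starts its first interval at randomization, as its closing sentence implies, with the 280-day limit of Table 8.

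| Death on day | No-assessment sentence | US text (rule D, Appendix 6.1) | Other Regions text (item 3) |
|---|---|---|---|
| 60 | censored at day 0 | 60 is within 280: event | event |
| 200 | censored at day 0 | 200 is within 280: event | event |
| 300 | censored at day 0 | 300 exceeds 280: censored at randomization | event |

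The 280 days is itself an inference: the first window in Table 8 starts at Day 2, and there is no row for randomization.

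**2. The plan's power.** Inputs from SAP 1.3: 200 events, HR 0.60, 1-sided alpha 0.025 overall and 0.024 at the primary analysis; 3:1 allocation from SAP 1.6.2. Power = Φ(√(200 × 0.75 × 0.25) × |ln 0.60| − z) = Φ(6.124 × 0.511 − z). This gives 87.9% at alpha 0.025 and 87.5% at 0.024, against about 87% stated. The plan's figure reproduces.

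**3. Deaths at stake.** The documents give no early-death count, so I use their OS assumptions with an exponential distribution.

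- Arm B hazard: −ln(0.73)/36 = 0.00874 per month (median 79.29 months, as stated). Arm A: 0.6 times this.
- First scheduled scan: Cycle 5, 16 weeks = 112 days = 3.68 months (Protocol 8.2.1.10).
- Subjects: 445 at 3:1, about 334 and 111.
- Arm B: 111 × (1 − exp(−0.00874 × 3.68)) = 111 × 3.17% = 3.5.
- Arm A: 334 × (1 − exp(−0.6 × 0.00874 × 3.68)) = 334 × 1.91% = 6.4.
- Total 9.9, or 9.9/200 = 5% of events. With equal early hazards (assumption): 445 × 3.17% = 14.1, or 7%.

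This is an upper bound for that window, because Protocol 8.2.2 allows a scan at any time for suspected progression. The sentence also reaches beyond the window: it catches an unscanned subject who dies later, and one with no baseline assessment who dies at any time.

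**4. Power if the events were simply lost.** At alpha 0.024, 190 events give 85.8% and 186 give 85.1%, against 87.5%. If the trial waits for 200 counted events, power is essentially kept and the question becomes bias.

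**5. Bias.** Simulation with PFS HR 0.60, control median 28 months, 445 subjects, cutoff at 200 counted events, unstratified log-rank test at 0.024. Uniform accrual over 50 months is assumed, and so are the early-death rates, except those in the first row.

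| Early deaths, A vs B | Power, counted | Power, dropped |
|---|---|---|
| 1.9% vs 3.2% (plan's OS assumptions) | 90% | 90% |
| 3.2% vs 3.2% | 86% | about 90% |
| 4% vs 2% | 79% | 90% |

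In the first row the estimated HR is 0.56 either way. A similar run with 440 subjects moves the HR from 0.59 to 0.56 when the early-death HR is 1, and from 0.65 to 0.56 when it is 2. The one-step estimate used here returns about 0.56 for a true 0.60, so only the differences between counted and dropped should be read.

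**The case against.** The best defence is that the intention is clear. The event definition needs no scan, the Primary Analysis entry censors only those without an event, rule C and item 3 count deaths without a scan condition, and Appendix 6.1 measures the gap to death. The same no-assessment sentence appears under TTP, where death is not an event and the sentence fits, so it may simply be shared text. OS counts every death in any case.

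Much of this stands. A reader might infer that the plan excludes all deaths in the first 16 weeks from PFS. The documents do not support that: most of the text points to counting them, and a subject scanned early for suspected progression is outside the sentence altogether. Nor does any section support the idea that these deaths are mainly treatment-related.

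What the defence does not supply is an order of precedence. This SAP does censor some deaths because scans were missed (rule D), so a programmer cannot assume that death always overrides. The protocol writes the survival condition into one sentence and leaves it out of the next. The SAP takes precedence over the protocol but has the same gap.

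**Conclusion.** The sentence is wrong as written. Followed literally, it gives a PFS status that contradicts the endpoint's own definition, and nothing in either document resolves the conflict.

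The numbers affected are modest: at most about 10 deaths before the first scheduled scan under the plan's OS assumptions, or 14 with equal early hazards, plus any later deaths in unscanned subjects. If early deaths follow the plan's assumptions, the effect on the HR and on power is negligible. If they are in excess in Arm A, dropping them favours Arm A; the fall from 90% to 79% when they are counted rests on assumed rates of 4% and 2%.

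A reader might also quote a sharper gain in the chance of success. With a true PFS HR of 0.70 and the same 4% against 2%, it is 47% if the deaths are counted and 64% if they are dropped. That requires a weaker effect than the planned 0.60 and an early excess in Arm A, where the plan's own OS assumptions give the opposite imbalance. It illustrates sensitivity and is not an expected size.

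**What to change.** Before the sponsor is unblinded for the primary PFS analysis, reword the Table 6 sentence along these lines: *A subject without a PFS event who lacks a baseline or a post-baseline assessment is censored at randomization. A death before any post-baseline assessment is a PFS event on the date of death.* The existing rule on subsequent anticancer therapy stays as it is.

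For the US analysis, add that rule D and Appendix 6.1 apply with randomization as the start of the first interval, and state the maximum gap for it. This is 280 days if the first time period of Table 8 is used. Apply the same wording to IRC-assessed PFS, and record in SAP 8.1 that the protocol sentence is superseded.

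The cost is a sentence or two in the SAP and a line of derivation code. Settling the point after unblinding would look data-driven.

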2.3. Exploratory Objective(s)

- To compare treatment groups with regards to patient reported lymphoma symptoms and health-related QOL as measured by the Functional Assessment of Cancer Therapy-Lymphoma (FACT-Lym)
- To characterize the pharmacokinetics of ibrutinib and rituximab and explore the potential relationships between ibrutinib metrics of exposure with relevant clinical or biomarker information
- To evaluate and/or identify patient populations defined by relevant biomarker(s)
- To evaluate the minimal residual disease (MRD)-negative rate defined as the proportion of follicular lymphoma subjects who achieve a CR and who reach MRD-negative disease status

- To evaluate whether the addition of ibrutinib to rituximab will result in improvement of the investigator-assessed CR30 when compared with rituximab alone in treatment naïve subjects with follicular lymphoma

The statistical analysis methods and final set of exploratory endpoints are detailed in the Statistical Analysis Plan (SAP); if there are any variances between both documents the SAP takes precedence.

[figure not shown]

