# 1 INTRODUCTION

The statistical analysis plan (SAP) version 7.0 is based on the protocol amendment 4 dated February 07, 2023. This SAP defines key elements including variable definitions, and statistical methods for analysis of data in evaluation of efficacy and safety of PCYC-1141-CA. Analyses of biomarker and pharmacokinetics (PK) data are not in the scope of this document.

[figure not shown]
Throughout this SAP, "study treatment" and "study drug" are used interchangeably, and both are referring to ibrutinib, placebo, and/or rituximab.

Analysis methods specified in this document take precedence over those described in the protocol should there be any differences.

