### 1.2.3 Exploratory Endpoints

- Health-related quality of life (QOL) as measured by the FACT-Lym
- Pharmacokinetic parameters or metrics of systemic exposure of ibrutinib and rituximab
- Evaluation and/or identification of relevant patient populations defined by biomarker(s)
- Minimal residual disease (MRD)-negative rate defined as the proportion of FL subjects who achieve a CR and who reach MRD-negative disease status
- Complete response rate at 30 months (CR30) as defined by the International Working Group (IWG) Revised Response Criteria for Malignant Lymphoma ([Cheson 2014](#))
- Time to Progression (TTP) as assessed by investigator
- Duration of Complete Response (DOCR) as assessed by investigator

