Endpoint	Definition	Analysis Method
Exploratory Endpoints		
CR30	The proportion of subjects achieving a best overall response of CR per investigator assessment at or prior to 30 months and at or prior to initiation of subsequent anti-cancer therapy.	Chi-square test, rate ratio and 95% CI. For each treatment, Clopper-Pearson method is used for 95% CI of the estimated proportion.
MRD negativity rate	The proportion of follicular lymphoma subjects who achieve a CR and who reach MRD-negative disease status.	Chi-square test or Fisher's exact test depending on the sample size, rate ratio and 95% CI for each treatment (Clopper-Pearson method).
FACT-Lym total score and subscale scores	Change from baseline by visit regardless of initiation of subsequent anti-cancer therapy, proportion of subjects achieving clinically meaningful improvement or worsening on or prior to initiation of subsequent anti-cancer therapy, time to improvement or worsening on or prior to initiation of subsequent anti-cancer therapy. Clinically meaningful improvement is defined as an increase from baseline $\geq 7$ points for FACT-Lym total score, ( $\geq 6$ points for Trial Outcome Index, $\geq 3$ points for lymphoma subscale score). Clinically meaningful worsening is defined as a reduction from baseline $\geq 5$ points for lymphoma subscale score, ( $\geq 6$ points for Trial Outcome Index.)	
Descriptive summary statistics. The proportion of subjects achieving clinically meaningful improvement or worsening will be compared between the two randomized treatment arms using chi-square test. 95% CI for the rate ratio will be calculated. For each parameter, change from baseline will be analyzed using the Mixed-Effects Model Repeated Measure (MMRM). The model includes the continuous baseline scores, and categorical fixed effects of pre-specified stratification factors, treatment, time point and treatment-by-time point interaction. An unstructured variance covariance matrix will be used. Kenward-Roger's approximation will be used to estimate denominator degrees of freedom. The 2-sided 95% CIs will be calculated for the least square means.
 
Time to event analyses will be conducted for the time to improvement/worsening endpoints. Subjects who have not met the definition of improvement/worsening will be censored at the last non-missing post-baseline PRO assessment prior to or on the date of initiating subsequent anti-cancer therapy.

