**Table 8. Algorithm for defining  $\geq 2$  consecutive missing assessments**

Time Period	Adequate Non-PD Assessment		Imaging Schedule for the Two Subsequent Consecutive Assessments after the Adequate Non-PD Date	Maximum gap & in Days Allowed between the Adequate Non-PD Date and Next Adequate Assessment or Death
	Scheduled Visit	Study Day Time Period Window #		
1	Cycle 5 to Cycle 29	Day 2 - Day 841	every 4 cycles (112 days)	$280 = (112+28)*2$
2	Cycle 33	Day 842 - Day 953	4 cycles (112 days) & 6 cycles (168 days)	$336 = (112+28) + (168+28)$
3	Cycle 37 and up	Day 954 and up	every 6 cycles (168 days)	$392 = (168+28)*2$

#: The visit window for each visit is based on the midpoint between two scheduled visits (i.e. target day +/- the half planned interval between two scheduled visits). The study day in time period 1 can be as early as one day after randomization (Day 2). If the adequate non PD assessment is the same as or earlier than the midpoint, it will be assigned to the earlier visit, and if the assessment is later than the midpoint, it will be assigned to the later visit. Study day is calculated in reference to the randomization date. 1 cycle = 28 days.

&: A 28 day window is allowed to provide more flexibility regarding the timing of the data collection for disease assessment considering the COVID 19 situation and the indolence of first line follicular lymphoma

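### CR30 is named the complete response rate at 30 months, but SAP Table 6 computes a cumulative best response of CR by 30 months, so complete responders who later progress or die still count as successes

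*SAP*

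**What the plan says.** SAP section 1.2.3 lists the endpoint as "Complete response rate at 30 months (CR30) as defined by the International Working Group (IWG) Revised Response Criteria for Malignant Lymphoma", and the protocol's endpoint list (section 10.2.3 and the synopsis) names it the same way. Protocol section 2.3 makes it a between-arm question: "improvement of the investigator-assessed CR30 when compared with rituximab alone".

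The working definition is in SAP Table 6: "The proportion of subjects achieving a best overall response of CR per investigator assessment at or prior to 30 months", with one further condition, "and at or prior to initiation of subsequent anti-cancer therapy". The planned analysis is "Chi-square test, rate ratio and 95% CI", with Clopper-Pearson intervals for each arm. SAP section 4 makes the ITT population the default for endpoint analyses, so the denominator is all randomized subjects.

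The row does not require CR to be present at the 30-month assessment, and it does not make a subject a non-responder for progression or death after CR. No other section of either document adds such a rule. SAP section 8.1, which lists changes from the protocol's planned analyses, does not mention CR30.

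**The concern.** A rate at 30 months reads as a landmark: who is in complete response at that time. A best response up to 30 months is a running maximum that cannot worsen once CR has been reached. The two agree only if no complete responder loses the response before month 30.

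What is at stake is the meaning of a reported figure. A reader of the study report would take CR30 as the share of randomized subjects in CR at two and a half years. The figure would include subjects who had already relapsed or died. The between-arm test would likewise compare how often CR was ever reached, not how often it was still present.

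**Working it through.** The documents give no CR30 rate, power or sample size, so there is no CR30 figure to reproduce. The check is mainly one of definitions.

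**Name against rule for four example subjects**

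| Course up to month 30 | CR at month 30? | Success under Table 6? |
|---|---|---|
| CR at Cycle 5, still in CR at month 30 | Yes | Yes |
| CR at Cycle 5, progression or death at month 12 | No | Yes |
| PR only, progression at month 12 | No | No |
| Subsequent therapy first, CR afterwards | Excluded by either rule | No |

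Only the second row is miscounted. Every subject in CR at month 30 without earlier progression or subsequent therapy also has a best response of CR by month 30. The Table 6 rate is therefore equal to or greater than the landmark rate in each arm.

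**Is there an assessment near 30 months?** Protocol section 8.2.1.10 schedules response visits at Cycles 29, 33 and 37. With 28-day cycles:
- Cycle 33 Day 1 = 28 × 32 + 1 = Day 897, which is 896 / 30.44 = 29.4 months after Cycle 1 Day 1.
- SAP Table 8 already maps "Day 842 - Day 953" to Cycle 33. The limits are the midpoints to Cycle 29 (Day 785) and Cycle 37 (Day 1009): (785 + 897) / 2 = 841 and (897 + 1009) / 2 = 953.
- Thirty months is 30 × 30.44 = about Day 913, inside that window.

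**Can the gap be sized?** In each arm, gap = (ever-CR rate) × (share of complete responders lost by month 30). The documents supply neither factor for this trial. The following is illustration only.

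Inputs from SAP section 1.3: control median PFS 28 months and HR 0.60. As a check on them, the Schoenfeld formula with 200 events, 3:1 allocation and one-sided alpha 0.024 gives power 0.875, against about 87% stated. Under exponential PFS, 30-month PFS is exp(−ln 2 × 30 / 28) = 47.6% in Arm B and exp(−0.60 × ln 2 × 30 / 28) = 64.0% in Arm A.

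Assumptions not in the documents: first CR at Cycle 5 (112 / 30.44 = 3.7 months), and a hazard after CR of 0.25 to 1.0 times the design PFS hazard.
- Loss by month 30 in Arm B: 1 − exp(−f × ln 2 × 26.3 / 28) = 15% (f = 0.25) to 48% (f = 1).
- Loss in Arm A, with the hazard multiplied by 0.60: 9% to 32%.
- If ever-CR rates are equal in the two arms, the Table 6 rate ratio is 1.00 and the landmark ratio is 0.91 / 0.85 = 1.07 to 0.68 / 0.52 = 1.30. With first CR at Cycle 13 it is 1.05 to 1.21.

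The ratio moves only because the HR of 0.60 is assumed to carry over to the period after CR. The direction in percentage points is not fixed either:
- Ever-CR 40% in both arms, upper losses: 0.40 × 32% = 12.8 points in A and 0.40 × 48% = 19.2 points in B.
- Ever-CR 40% in A (Arm 1 of the Phase 2 study) and 25% in B (the 6-month investigator rate for rituximab alone in the lenalidomide trial, both in Protocol section 1.4), upper losses: 12.8 points in A and 0.25 × 48% = 12.0 points in B.
- The same CR rates with lower losses: 0.40 × 9% = 3.6 points in A and 0.25 × 15% = 3.75 points in B.

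**The case against.** The strongest reply is that the plan is explicit and only its label is loose. The one-line endpoint names say how CR is judged, Table 6 is the only operational definition, and the SAP states that "Analysis methods specified in this document take precedence over those described in the protocol should there be any differences". Protocol section 2.3 also leaves the final exploratory endpoints to the SAP. This settles which rule will be run. It does not make the name right, because the SAP itself uses the landmark name in section 1.2.3 and the cumulative rule in Table 6.

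Second, a reader might infer that the trial would miss a difference in durability. The documents do not support that. Table 6 also has duration of complete response (DOCR), duration of response (DOR) and PFS. What remains is narrower: DOCR covers only subjects who reached CR, so it is not a comparison of all randomized subjects, which a landmark CR rate would be.

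Third, a reader might apply an assumed 10–25% loss to the Phase 2 CR rates of 40–50% and conclude that the figure is 4 to 12.5 points too high, more so in the control arm. The loss rate is an assumption. The Phase 2 data come from ibrutinib plus rituximab only, and their 30-month PFS is for whole arms, not complete responders. The direction in points can go either way, as shown above. Nor is there a contrast from rituximab stopping, since maintenance ends at about two years in both arms.

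Fourth, a landmark rule has practical difficulties. CR may be confirmed by PET at one visit and followed by CT only. Visits were disrupted by COVID-19 and the conflict in Ukraine. The Table 8 window was built to detect missed PFS assessments. The first is met by using the overall response that the investigator already records at each response visit. The second needs a stated missing-data rule. The third is no bar to borrowing the window.

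**Conclusion.** The point holds as a mismatch between name and computation. As written, CR30 will be a rate of CR ever reached by 30 months, and in each arm it can only equal or exceed the rate of CR present at 30 months. The size of the excess and its direction between arms cannot be derived from the documents. The illustrative ranges rest on assumed CR timing and an assumed hazard after CR.

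The consequence is limited. CR30 is exploratory and outside the tested sequence of PFS, ORR, OS and infusion-related reactions, so no confirmatory conclusion changes. The stronger readings, that durability goes unmeasured or that a known number of points is added to one arm, are not supported. This is a minor point that is worth correcting because the remedy is cheap.

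**What to change.** In Table 6, define CR30 over all randomized subjects as an investigator overall response of CR at the assessment mapped to Cycle 33 (target Day 897, window Day 842 to 953, taking the assessment closest to the target), with no earlier PD, death or subsequent anti-cancer therapy. Count a missing assessment as non-CR, report the number missing by arm, and add a sensitivity analysis for visits missed through COVID-19 or the conflict. Keep the current quantity under the label *best response of CR by 30 months*, and list the change in SAP section 8.1.

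No new data are needed. Cycle 33 is a scheduled response visit, and Protocol section 8.3.1 keeps subjects who stop without PD on 16-weekly follow-up to the planned Cycle 37 date. Enrollment was complete as of July 1, 2021, so the last subject's month 30 fell no later than about January 2024, before SAP version 7.0 of May 2024.

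The cost is one extra derivation and a lower stated rate. The window runs to Day 953, slightly past month 30 (about Day 913), so a first CR in that interval would count under the new rule but not the old; state this in the definition. If arm-level results are already known, label the landmark version post hoc. If no derivation is to be added, relabelling the present row is the minimum.
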